13 DATA ANALYSIS AND STATISTICAL ISSUES/JUSTIFICATION FOR STUDY DESIGN

13.1 General Statistical Analysis Plan:

The HM3 IDE study will investigate the safety and effectiveness of the HM3 LVAS for short term hemodynamic support, such as a bridge to cardiac transplantation (BTT) or myocardial recovery, or as long term support, such as destination therapy (DT). The HM3 IDE study is a prospective, multicenter, unblinded, randomized, controlled, non-inferiority study comparing the HM3 LVAS to the HM II LVAS.

In general, continuous data will be presented as the number of Subjects, mean with standard deviation, median, and minimum and maximum values. Categorical data will be reported as frequencies and percentages. Adverse events will also be reported as rates per patient year. Only adverse events that occur after the start of the implant procedure will be analyzed. Survival data will be presented using the Kaplan-Meier product limit method.

Data will be analyzed using the intent-to-treat method (ITT) defined as all randomized Subjects. Every effort will be made to avoid cross-over but in the event they occur, data will also be analyzed “as randomized” for efficacy analysis and “as treated” for safety analysis and all other secondary endpoints.

Every effort will be made to collect all required data. Missing primary endpoints will be imputed using multiple imputation techniques. Missing secondary endpoints will not be imputed, except as described below. A one-sided 0.025 level of significance or two-sided 0.05 level of significance will be used to declare statistical significance as outlined below. Multiplicity adjustments will not be made unless specified below.

Statistical analysis will be performed using SAS version 9.1 or higher.

13.2 Analysis Populations

13.2.1 Intent-to-treat: All Randomized Subjects

This is the primary analysis population for the primary endpoint. Subjects are analyzed under the treatment to which they were randomized.

13.2.2 As Treated: All Treated Subjects

This is the primary analysis population for the secondary endpoints. Subjects are analyzed under the treatment they received.

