10.3 Powered Secondary Endpoint

- Incidence of pump replacements at 24 months

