13.16.2 KCCQ

The KCCQ score will be assessed at baseline and then at 3, 6, 12, 18, and 24 months. Data will be analyzed using mixed modeling by comparing the KCCQ score at each assessment interval to the baseline score. The Short Term indication will be limited to the 3 and 6 month assessments. The Long Term indication will include all assessments until 24 months or outcome, whichever occurs first.

13.17 Powered secondary analysis:

In addition to the primary outcome, the study will be powered to test if HM3 pump reliability is superior to HM II by analyzing the incidence of pump replacements. Randomization described in Section 13.4 will continue beyond the Subjects needed to power the primary endpoint until a sufficient sample size has been enrolled to test the secondary endpoint. The null and alternative hypotheses are:

$$H_0: \pi_{HM3} \geq \pi_{HM II}$$

$$H_A: \pi_{HM3} < \pi_{HM II}$$

where π_{HM3} is the HM3 pump replacement rate and $\pi_{HM II}$ is the HM II pump replacement rate.

Based on data contained in Thoratec's device tracking database, 7% of the HM II Subjects receive a pump replacement by 24 months. If we assume that HM3 pump replacements will be reduced to 3% at 24 months, then 1028 Subjects will be needed to prove superiority with a power of 80% and alpha = 0.05 (2-sided).

Once the 366 Subjects needed for the long term indication are enrolled, Thoratec will continue to randomize 662 more Subjects for this secondary analysis. Data for this secondary analysis is not needed for the short or long term indications, but rather will be used to provide additional labeling information.

The Subjects will be followed for 24 months or to outcome, whichever occurs first, and analyzed using the Fisher's exact test. Treatments will also be compared on time-to-pump replacement using the log-rank test where Subjects without a replacement are censored at last known follow-up. Otherwise, there will be no imputation of missing data for this analysis.

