29.2 Device Accountability Records

The Thoratec HeartMate 3 LVAS is an investigational device. All investigational devices must be stored in a location that is accessible only by authorized study personnel. The Sponsor and investigator must maintain accurate Device Accountability records indicating the date of shipment, receipt of product, date of use and assignment to study Subject, and final disposition (return) of the devices.

Traceability of investigational devices will be maintained by the Sponsor through the use of unique serial and/or lot numbers.

All unused investigational components must be returned to the Sponsor, as directed.

NOTE: Investigational devices should only be used on Subjects who are enrolled in the study and randomized to the HM3 arm.

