8.1.2 As Treated: All Treated Subjects

This is the primary analysis population for the secondary endpoints. Subjects are analyzed under the treatment they actually receive.

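### No analysis population is named for the powered superiority test on pump replacement, so it defaults to As Treated rather than to the randomized groups

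*Protocol*

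**What the plan says.** Protocol 10.3 lists the powered secondary endpoint: "Incidence of pump replacements at 24 months". Protocol 13.17 says that "the study will be powered to test if HM3 pump reliability is superior to HM II by analyzing the incidence of pump replacements". It gives the hypotheses, Fisher's exact test, a two-sided alpha of 0.05 and 1028 subjects, and says the result is for labeling. SAP 8.16 repeats this with 514 per arm. Neither section says which subjects are analyzed or under which arm.

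The population rules are elsewhere:

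- Protocol 13.2.1 and SAP 8.1.1 make intent-to-treat primary for the primary endpoint.
- Protocol 13.2.2 says of As Treated: "This is the primary analysis population for the secondary endpoints. Subjects are analyzed under the treatment they received". SAP 8.1.2 has the same rule: "Subjects are analyzed under the treatment they actually receive".
- Protocol 13.1 and SAP section 8 first name intent-to-treat as the method for the data in general. They then add that, if cross-over occurs, safety and the other secondary endpoints will also be analyzed as treated.

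Protocol 29.2 limits who may receive the new pump: "Investigational devices should only be used on Subjects who are enrolled in the study and randomized to the HM3 arm". HM II is described in Protocol section 1 as FDA-approved and carries no such limit. Protocol section 5 describes the trial as unblinded.

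**The concern.** This is the only secondary endpoint for which the trial is powered, and 662 subjects beyond the primary cohort of 366 are randomized for it. The reason to randomize them is to compare like with like. If subjects are then grouped by the device they received, anyone whose device was changed after allocation moves to the other group, and their outcome moves with them. Because allocation is known, such a change may be related to the patient's condition.

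The cross-over that the protocol permits has one direction. A subject randomized to HM3 may receive HM II; a subject randomized to HM II who received HM3 would be a protocol deviation. Under As Treated, permitted movers leave the HM3 denominator and join HM II, and any replacement among them is counted against HM II. At stake is whether a labeling statement of superiority rests on the randomized comparison, and whether the population could be settled only after the data are known.

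**Working it through.** **Plan's own figure.** Inputs from Protocol 13.17: for the control, "7% of the HM II Subjects receive a pump replacement by 24 months"; for HM3, an assumed 3%; two-sided alpha 0.05; power 80%. The mean rate is 5% and the difference 0.04.

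- Uncorrected: n = [1.960·√(2·0.05·0.95) + 0.842·√(0.07·0.93 + 0.03·0.97)]² / 0.04² = (0.604 + 0.258)² / 0.0016 ≈ 464.8, so 465 per arm (930 in total).
- With continuity correction: n' = (n/4)·[1 + √(1 + 4/(n·0.04))]² = 116.2 × (1 + 1.102)² ≈ 513.6, so 514 per arm, 1028 in total.

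The stated 1028 reproduces. Exact Fisher power at 514 per arm is 81.6%. The calculation has no allowance for cross-over.

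**Illustration.** Suppose 22 replacements among 514 randomized to HM3 and 36 among 514 randomized to HM II. With c movers from HM3 to HM II, of whom r have a replacement, the As Treated table is (22 − r)/(514 − c) v (36 + r)/(514 + c). The documents give no cross-over rate and no risk for movers, so c and r are both assumptions.

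| Movers c | Replacements r | HM3 v HM II | Fisher p |
|---|---|---|---|
| 0 (randomized arms) | – | 22/514 v 36/514 | 0.078 |
| 5 | 0 | 22/509 v 36/519 | 0.079 |
| 5 | 1 | 21/509 v 37/519 | 0.042 |
| 10 | 0 | 22/504 v 36/524 | 0.104 |
| 10 | 1 | 21/504 v 37/524 | 0.058 |
| 10 | 2 | 20/504 v 38/524 | 0.030 |

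The two rows that cross 0.05 give movers a replacement risk of 20%. The overall rate in the example is 58/1028 = 5.6%, so movers are at about 3.5 times average.

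**False-positive rate in favour of HM3.** Assume no true difference, 7% replacement in both randomized arms, and movers at k times average risk. The table gives the exact probability that Fisher's test rejects in favour of HM3; the nominal value is 2.5%.

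| Movers | k = 1 | k = 2 | k = 3 |
|---|---|---|---|
| 0 (same as intent-to-treat) | 1.9% | – | – |
| 5 (1%) | 2.3% | 2.8% | 3.4% |
| 10 (2%) | 2.1% | 3.1% | 4.4% |
| 26 (5%) | 2.1% | 5.6% | 12.7% |

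At average risk the rate stays below 2.5% whatever the number of movers shown. Inflation needs both above-average risk and more than a handful of movers.

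**Cost of intent-to-treat.** If movers carry the HM II risk of 7%, the HM3 arm rate becomes [(514 − c)·3% + c·7%]/514. Power from the uncorrected formula is 83.8% with no movers, 83.0% with 5 (3.04%), 82.1% with 10 (3.08%) and 79.1% with 26 (3.20%).

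**The case against.** The strongest reply is that the plan does not clearly choose As Treated here. The powered endpoint has its own headings (Protocol 10.3 and 13.17), apart from the ordinary secondary endpoints in 10.2 and 13.14. Protocol 13.1 names intent-to-treat first and presents the as-treated analysis as an addition. This stands in part: As Treated applies by default, not by an explicit statement for this test. But two defensible readings of a labeling test are themselves a reason to name the population.

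A reader might infer that the bias can run only toward HM3. The documents do not support that. They fix the permitted direction of cross-over, not the replacement risk of those who cross over. With ten movers and no replacements, p moves from 0.078 to 0.104, against HM3. Nor does Protocol 29.2 make the reverse cross-over impossible; it makes it a deviation.

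The illustration also starts near 0.05, where one event matters. Near the planned rates, 15 v 36 of 514 gives p = 0.0037, and five movers with one or no replacement leave it at 0.0014 or 0.0038.

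As Treated has a rationale for a question about pump reliability: intent-to-treat charges an HM II failure to the HM3 arm if the subject was randomized to HM3. That supports reporting it as a sensitivity analysis, not resting a superiority claim on it. Finally, Protocol 13.7.1 compares the arms on each component of the primary composite, which includes pump replacement. That covers the primary cohort of 366, not all 1028.

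**Conclusion.** The point holds as a gap in specification with a default that is weaker than it should be. The powered pump-replacement test has no stated population, and the rule that then applies gives up the randomized grouping in an unblinded trial. The bias can favour HM3 if movers have above-average replacement risk, is negligible at average risk, and runs against HM3 at lower risk. At about 1% cross-over the effect on the false-positive rate is small (at most 3.4% in the range shown); at 5% cross-over and two to three times average risk it reaches 5.6% to 12.7%. These sizes rest on assumed cross-over counts and risks. Both the plan's stated intention to avoid cross-over and the unknown rate argue for moderate weight.

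A related conflict belongs with this point. SAP section 7, item b, rules out statistical claims on secondary endpoints, while SAP 8.16 plans to prove superiority on one of them for labeling. The confirmatory standing of the test is therefore not settled by the text either.

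**What to change.** In Protocol 13.17 and SAP 8.16, state that the powered pump-replacement endpoint is analyzed primarily by intent-to-treat: all randomized subjects, in the arm to which they were randomized. Refer to Protocol 13.2.1 and SAP 8.1.1 by number, because the SAP's As Randomized set (8.1.3) is a different population that drops subjects who crossed over. Keep As Treated as a sensitivity analysis and report each cross-over with its reason. Amend SAP section 7, item b, so that it agrees with the standing given to this test in 8.16.

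The cost is about one sentence per document plus the edit to section 7, and the sample size stays at 1028. The price is slight dilution: about one to two percentage points of power for 5 to 10 cross-overs on the assumptions above, and slightly lower rates in both arms because never-implanted subjects enter the denominators.

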13.3 Study Hypothesis

13.3.1 Short Term Support:

The short term study endpoint is a composite of survival to transplant, myocardial recovery or 6 months of support (whichever occurs first) free of a debilitating stroke (modified Rankin Score > 3) or reoperation to replace the original pump. A Subject will be considered a success if they are:

- Electively transplanted or explanted for myocardial recovery prior to 6 months or
- Alive at 6 months, and
 - Have not experienced a stroke with a modified Rankin Score > 3, and
 - Have not received a device replacement or exchange, and
 - Have not received an urgent transplant due to a LVAS malfunction.

A Subject will be considered a failure if they:

- Expire prior to 6 months, or
- Experience a stroke with a modified Rankin Score > 3 prior to 6 months, or
- Have a device replaced or exchanged or deactivated for reasons other than myocardial recovery prior to 6 months, or
- Have received an urgent transplant due to a LVAS malfunction prior to 6 months, or
- Have withdrawn from the study for any reason prior to 6 months

HM3 short term success rate will be compared to that of the HM II control in a non-inferiority manner. The null and alternative hypotheses are:

$$H_0: \pi_{HM3} \leq \pi_{HM II} - \Delta$$

$$H_A: \pi_{HM3} > \pi_{HM II} - \Delta$$

where π_{HM3} and $\pi_{HM II}$ are the short term success rates of HM3 and HM II, respectively, and where Δ is the non-inferiority margin.

13.3.2 Long Term Support:

The long term study endpoint is a composite of survival to transplant, myocardial recovery or 24 months of support (whichever occurs first) free of a debilitating stroke (modified Rankin Score > 3) or reoperation to replace the original pump. A Subject will be considered a success if they are:

- Electively transplanted or explanted for myocardial recovery prior to 24 months or
- Alive at 24 months, and
 - Have not experienced a stroke with a modified Rankin Score > 3, and
 - Have not received a device replacement or exchange, and
 - Have not received an urgent transplant due to a device malfunction.

A Subject will be considered a failure if they:

- Expire prior to 24 months, or
- Experience a stroke with a modified Rankin Score > 3 prior to 24 months, or
- Have a device replaced or exchanged or deactivated for any reason other than myocardial recovery prior to 24 months, or
- Have received an urgent transplant due to a LVAS malfunction prior to 24 months, or
- Have withdrawn from the study for any reason prior to 24 months

The 24 month success rate of the HM3 Subjects will be compared to the HM II control. The null and alternative hypotheses are:

$$H_0: \pi_{HM3} \leq \pi_{HM II} - \Delta$$

$$H_A: \pi_{HM3} > \pi_{HM II} - \Delta$$

where π_{HM3} and $\pi_{HM II}$ are the long term success rates of HM3 and HM II, respectively, and where Δ is the non-inferiority margin.

13.4 Randomization

Subjects will be randomized in a 1:1 fashion (1 HM3: 1 HM II). The randomization will be stratified by study center and blocked to maintain the 1:1 ratio over time. Randomization will be implemented through the Electronic Data Capture (EDC) system. Study centers will be allowed a maximum of 50 randomized Subjects. Centers may have their maximum enrollment number increased with prior Sponsor approval. An analysis will be conducted to determine if there is site bias. Subjects will be considered enrolled in the study upon signing informed consent; all subjects will be randomized and will be included in the intent-to-treat analysis.

13.5 Sample Size

13.5.1 Assumptions

- Larger gap between the rotor and pump housing in the HM3 may result in less thrombus than HM II
- Larger gap between the rotor and pump housing in the HM3 may result in less pump replacement due to ingested thrombus than HM II
- HM3 modular driveline may reduce pump replacements due to driveline damage or fatigue.

13.5.2 Short Term Indication

Based on a review of recent INTERMACS and Thoratec data, it is assumed that the HM II will achieve a composite success rate of 85% at 6 months. It is also assumed that the HM3 will have a composite success rate of 87% due to less pump replacements at 6 months caused by thrombus or driveline issues. It will take 276 total Subjects to achieve 80% power to prove the HM3 is non-inferior to HM II when the margin of non-inferiority is -10% ($=\Delta$ in the above null and alternative hypotheses) using the Farrington-Manning risk difference approach to non-inferiority at a one-sided alpha = 0.025.

INTERMACS HM II data from 26 sites likely to participate in the HM3 IDE study was reviewed. Eight hundred and twenty (820) patients were implanted with the HM II in 2012 at these sites and 52 (6%) received a transplant or explant due to myocardial recovery prior to 6 months. In order to have sufficient data to evaluate the 6 month success rate, an additional 9 Subjects will be randomized per arm (6% of 138) to account for these early outcomes. This results in 294 total Subjects.

13.5.3 Long Term Indication

Based on the results from the HM II Destination Therapy IDE study, it is assumed that 50% of the HM II Subjects will successfully achieve the composite primary endpoint. It is also assumed that the HM3 will have a composite success rate of 55% due to less pump replacements at 24 months caused by thrombus or driveline issues. It will take HM3348 total Subjects to achieve 80% power to prove the HM3 is non-inferior to HM II when the margin of non-inferiority ($=\Delta$ in the above null and alternative hypotheses) is -10% using the Farrington-Manning risk difference approach to non-inferiority at a one-sided $\alpha = 0.025$.

INTERMACS HM II data from 26 sites likely to participate in the HM3 IDE study was reviewed. Eight hundred and twenty (820) patients were implanted with the HM II in 2012 at these sites and 52 (6%) received a transplant or explant due to myocardial recovery prior to 6 months. In order to have sufficient data to evaluate the 24 month success rate, an additional 9 Subjects will be randomized per arm (6% of 138) to account for these early outcomes. This results in 366 total Subjects.

13.6 Early Safety Assessment

The HM3 IDE study will include an early safety assessment in lieu of a feasibility study. The first 10 HM3 Subjects enrolled in the study will be included and their data analyzed when they have achieved 30 days of support. A table describing the 30 days status of the Subjects will be prepared. Adverse events will be presented as the percentage of Subjects who experience the event, the number of events and the event rate per 30 days. The data will be presented to the DSMB and FDA for a recommendation to continue the study and to expand to remaining study centers. All Subjects included in the early safety assessment will continue to be followed per protocol and will be included in the final Short Term and Long Term analysis.

13.7 Analysis of Primary Endpoint

The HM3 will be considered non-inferior to the HM II for both short and long term indications if the lower two-sided 95% confidence limit of the risk difference in the composite success between treatment arms (HM3 minus HM II) is greater than -10% ("negative 10%", where 10% is the non-inferiority Δ in the above null and alternative hypotheses). Once non-inferiority is inferred, the data will be analyzed for superiority at a one-sided 0.025 level of significance using closed testing methods via the z-test of proportions using the normal approximation to the binomial distribution. Since the short term and long term evaluations are two distinct endpoints, no adjustment for multiple comparisons is required.

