13.12 Analysis of Pre-Implant Data

Tables will be created to define the study population at baseline. Tables will include demographics, all laboratory assessments, all hemodynamic assessment, cardiac history, INTERMACS profile, and concurrent interventions (Cardiac Resynchronization Therapy (CRT), Automatic Internal Cardiac Defibrillator (AICD), IABP, Inotropes, etc). The intended use of the device at implant will also be collected, as defined by INTERMACS (Appendix 6). Baseline data will be compared between treatment groups using unpaired t-tests or Fisher's exact test as appropriate.

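### The primary risk difference is crude and leaves collected baseline data unused: a cheap gain in precision is available, but nothing is wrong with the interval or the sample sizes

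*Protocol*

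**What the plan says.** **Primary analysis.** Protocol 13.7 and SAP 8.6 use the same criterion for both indications: the "lower two-sided 95% confidence limit of the risk difference in the composite success between treatment arms", HM3 minus HM II, must lie above -10%. The superiority step that follows is a "z-test of proportions using the normal approximation to the binomial distribution". Neither step names a stratum or covariate, and neither document specifies a covariate-adjusted sensitivity analysis.

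**Center.** Protocol 13.4 says: "The randomization will be stratified by study center and blocked to maintain the 1:1 ratio over time". Center then appears only in the treatment-by-site interaction model of Protocol 13.7.2 and SAP 8.6.2, where sites with fewer than 5 subjects are pooled.

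**Baseline data.** Age and intended use are screening items (Protocol 16.1). INTERMACS profile is a baseline item, assessed immediately before implant (Protocol 16.2; Table 2, footnote 18). All three are subgroup variables in Protocol 13.8 and SAP 8.7. Protocol 13.12 otherwise uses baseline data descriptively: "Tables will include demographics, all laboratory assessments, all hemodynamic assessment, cardiac history, INTERMACS profile, and concurrent interventions", with comparisons between arms.

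**Sizing.** Protocol 13.5.2 sizes the 6-month test "using the Farrington-Manning risk difference approach to non-inferiority at a one-sided alpha = 0.025". Protocol 13.5.3 and SAP 8.4.3 do the same at 24 months.

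**The concern.** If age or intended use predicts the composite, the crude difference carries chance imbalance that a model could remove. A standardized risk difference averages the model's predictions under each arm over all randomized subjects. It therefore estimates the same marginal quantity, and the hypotheses and the -10% margin are unchanged. Only the standard error shrinks.

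Both tests are planned at 80% power, so a device as good as assumed would still fail about one time in five. SAP 8.6 also allows the long-term evaluation only after short-term non-inferiority, so a chance miss at 6 months costs both indications. Precision from data already in hand is worth having in that setting.

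**Working it through.** **1. Inputs.** At 6 months, "HM II will achieve a composite success rate of 85% at 6 months" and "HM3 will have a composite success rate of 87"% for the new device; 147 per arm randomized. At 24 months, 50% and 55%; 183 per arm (SAP 8.4.3). Margin 0.10, one-sided alpha 0.025, 1:1 allocation.

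**2. Reproducing the plan's figure.** Farrington-Manning, per arm:

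n = [1.960 × √v0 + 0.8416 × √v1]² / D²

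Here D is the assumed difference plus 0.10, v1 is the summed binomial variance at the assumed rates, and v0 is the same at the rates fitted under the null.

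- 6 months: D = 0.02 + 0.10 = 0.12. v1 = 0.87 × 0.13 + 0.85 × 0.15 = 0.2406. The null-restricted rates are 0.794 and 0.894, so v0 = 0.2583. Then n = (0.9961 + 0.4128)² / 0.0144 = 137.9, or 138 per arm. This matches "It will take 276 total Subjects to achieve 80% power" exactly.
- 24 months: D = 0.15, v1 = 0.4975, v0 = 0.4938. Then n = 172.6, or 173 per arm (346), against a stated 348. The unpooled Wald formula gives 174 per arm, which is 348.

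**3. Power with covariates.** Power = Φ[(D√n − 1.960√v0) / √v1]. If the covariates explain a share R² of outcome variance, the variance is multiplied by (1 − R²), so n is replaced by n/(1 − R²). The documents give no R², so a range is shown.

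| R² (assumed) | 6 months, 147 per arm | 24 months, 183 per arm |
|---|---|---|
| 0 (crude) | 82.5% | 82.2% |
| 0.02 | 83.3% | 83.0% |
| 0.05 | 84.4% | 84.1% |
| 0.10 | 86.3% | 86.0% |
| 0.15 | 88.2% | 87.9% |

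For example, at 6 months with R² = 0.05, 147/0.95 = 154.7 and the power is 84.4%. At a fixed 80% power, R² of 0.05 to 0.15 is worth 14 to 40 subjects at 6 months and 16 to 52 at 24 months.

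**4. Center.** This was simulated with 65 centers of unequal size and blocks of 4 (both assumed), comparing the crude Wald limit with a Mantel-Haenszel difference. With up to 70 sites, a center averages 294/70 = 4.2 to 366/70 = 5.2 subjects.

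- Every center a stratum: with no center effect, power falls from 84.6% to 81.1% (6 months) and from 81.1% to 79.8% (24 months). With a between-center logit SD of 0.3, it falls from 84.6% to 82.2% and from 81.4% to 79.9%. Centers with only one arm drop out of the estimate.
- Sites under 5 pooled: the change is -0.5 to +0.5 points for an SD of 0 to 0.3. Gains above about 1 point appear only at an SD of 1.0 (6 months) or 0.6 to 1.0 (24 months).

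**5. How many covariates the data can carry.** Expected failures at 6 months are 147 × 0.15 + 147 × 0.13 = 41. INTERMACS profile has 7 levels and intended use 7 categories (Appendices 2 and 6). Entered in full with age and arm they take 6 + 6 + 1 + 1 = 14 parameters, about 3 failures each. With non-prognostic covariates and an uncorrected robust standard error, the simulated one-sided error of that model was 0.033 against 0.028 crude (6 months) and 0.031 against 0.025 (24 months).

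A two-covariate model (age and binary intended use, assumed effects, degrees-of-freedom correction) held the error at 0.022 to 0.027. It added about 0 to 1 point of power at 6 months and 0 to 2 points at 24 months.

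**The case against.** The strongest reply is that nothing needs correcting. The crude limit is valid under center-stratified randomization, the sample sizes reproduce, and power at the randomized sizes already exceeds 80%. All of that stands, and it is why this is an improvement rather than a defect.

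Three further points also stand:

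- **The gain is assumed.** Neither document reports the prognostic strength of any baseline variable. Simulations with a single risk score of AUC 0.66 to 0.75 took 24-month power from 81-83% to 86-89%. No such score exists in the plan, and that result does not carry over to a model with age and intended use.
- **INTERMACS profile may not be a pre-randomization value.** Randomization precedes implant, if possible within 72 hours (Protocol 16.1), and the profile is graded just before implant in an unblinded trial. It can be scored after the arm is known, and it has no scheduled assessment in subjects who are randomized but never implanted (a case foreseen in Protocol 22). Intended use has a milder form of the problem: Protocol 16.1 lists it at screening, while Table 2, footnote 11 refers to the time of implant.
- **The change has a cost.** SAP 8.6.3 computes conditional power and the revised sample size from an unadjusted Farrington-Manning statistic.

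A reader might also infer that omitting the randomization stratum throws away power or invalidates the test. The documents do not support this. Omitting center leaves the interval valid, or somewhat conservative if centers differ, and centers this small offer no dependable gain.

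**Conclusion.** The point holds as an efficiency recommendation. Both primary conclusions rest on a crude difference although usable prognostic data are collected on the subjects at screening.

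The likely benefit is roughly 0 to 1 point of power if the covariates are weak, and 2 to 6 points if R² is 0.05 to 0.15. The two-covariate check sits toward the low end. These figures rest on the plan's assumed success rates and on covariate effects that the documents do not supply. The simulations also assume center sizes and block length, and carry Monte Carlo error of about 0.7 points.

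The material does not support reading this as a flaw in the sample size or the confidence limit, as a reason to put center in the primary model, or as power available without cost.

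**What to change.** In Protocol 13.7 and SAP 8.6:

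- Make the primary estimate a g-computation (standardized) risk difference from a logistic model with arm, continuous age and intended use in two or three groups. State that only values recorded before randomization are used.
- Use a robust standard error with a degrees-of-freedom correction, and compare the lower 95% limit with -10%.
- Admit INTERMACS profile only if it is recorded before randomization and collapsed to a few levels. Leave center out of the primary model.
- Keep the crude risk difference as a sensitivity analysis.

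The cost is SAP text and standard code, with no new data, subjects or margin. Four items need care:

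- Covariates, groupings and the handling of missing baseline values must be fixed before unblinding, and so before the SAP 8.6.3 interim.
- The interim conditional power and re-estimation formulas must use the adjusted statistic, or the mismatch must be justified.
- The superiority z-test must be replaced by its adjusted counterpart.
- The multiple imputation of missing primary endpoints (Protocol 13.1; SAP section 7) must be made compatible with the adjusted model.
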